17.1	Adverse Events (AEs).....	21
17.2	Adverse Reaction (ARs).....	21
17.3	Notification and reporting of Adverse Events and Reactions	21
17.4	Serious Adverse Events (SAEs) or reactions	21
17.5	Notification and reporting of Serious Adverse Events.....	21
17.6	Urgent Safety Measures.....	22
17.7	Annual Safety Reporting	22
17.8	Overview of the Safety Reporting responsibilities.....	22
18.	Monitoring and auditing	22
19.	Trial committees	23
20.	Finance and funding	23
21.	Indemnity.....	23
22.	Dissemination of research findings	23
23.	References	24

2. Glossary

AE	Adverse Event
AR	Adverse Reaction
ASR	Annual Safety Report
BMI	Body Mass Index
CAP	Controlled Attenuation Parameter
CI	Chief Investigator
CRF	Case Report Form
CyTOF	Mass Cytometry
FNA	Fine Needle Aspirate
GLP-1	Glucagon Like Peptide 1
HOMA-IR	Homeostatic Model Assessment of Insulin Resistance
HRA	Health Research Authority
JRMO	Joint Research Management Office
NAFLD	Non-alcoholic fatty liver disease
NASH	Non-alcoholic Steatohepatitis
NIHR	National Institute for Health Research
Participant	An individual who takes part in a clinical trial
PI	Principle Investigator
PIS	Patient Information Sheet
REC	Research Ethics Committee
T2DM	Type 2 Diabetes Mellitus

3. Signature page

Chief Investigator Agreement

The study as detailed within this research protocol will be conducted in accordance with the principles of Good Clinical Practice, the UK Policy Framework for Health and Social Care Research, and the Declaration of Helsinki and any other applicable regulations. I agree to take responsibility for the statistical analysis and oversight of this study.

Chief Investigator Name: [name]

Signature:

Date: 04/09/2018

4. Summary and synopsis

Short title	Investigating mechanisms in non-alcoholic fatty liver disease
Methodology	Cross-sectional study
Research sites	Barts Health NHS Trust, Homerton University Hospital NHS Foundation Trust Kings College Hospital, NHS Foundation Trust Bromley by Bow Centre
Objectives / aims	To identify key characteristics of the tissue resident and peripherally circulating immune-phenotype in addition to blood markers, metabolic profile, faecal and oral microbiota in non-alcoholic fatty liver disease within an ethnically diverse population
Number of participants	153
Inclusion and exclusion criteria	Over 18 years of age Confirmed Non-alcoholic Fatty Liver disease or Healthy Control Excluding participants with type 1 Diabetes Mellitus or immune-suppressant concomitant medication or auto-immune disease or excessive alcohol intake
Statistical methodology and analysis	Comparative and descriptive
Study duration	24 months

5. Introduction

5.1 Background and Rationale

Non-alcoholic fatty liver disease (NAFLD) is a major cause of morbidity and mortality worldwide. NAFLD is the hepatic manifestation of the metabolic syndrome and is strongly associated with type 2 diabetes mellitus, obesity, hypertension and hypercholesterolaemia. It affects 20-30% of the general population, 58% of overweight individuals, 70% of diabetics and almost 90% of obese individuals.¹

NAFLD reflects a spectrum of disease from simple steatosis without inflammation and 12-20% of individuals with NAFLD who develop the aggressive form of disease, non-alcoholic steatohepatitis (NASH). This is characterised by liver cell death, inflammation and fibrosis which can lead to cirrhosis, liver failure and liver cancer². It is recognised that NASH with fibrosis confers increased all-cause and liver-related mortality over simple steatosis or NASH without fibrosis.²⁻⁴ Cardiovascular disease dominates non-liver related mortality and this risk appears to be independent to the presence of metabolic syndrome.

Classically NAFLD is associated with an elevated Body Mass Index (BMI), a well-recognised measure of obesity. However, studies have identified that people of south Asian ethnicity develop NAFLD with a BMI outside of the 'obese' range.^{5,6} Factors possibly involved in this observed phenomenon includes preponderance for insulin resistance⁷ and a distinct genetic profile.⁸

Apart from performing a liver biopsy, there is no convenient or accurate way to distinguish patients who have NASH from those who have simple steatosis which does not progress. This is largely because the pathogenesis of NASH is not fully understood. Hepatic fat deposition, genetic abnormalities, oxidative stress, inflammatory cytokines and more recently bacterial dysbiosis have all been shown to be relevant, but, the mechanisms that link these phenomena to NASH have not been elucidated^{9,10}. For the same reasons, there are currently no drugs licensed for the treatment of NASH and prevention of its complications. Therefore the cornerstone of treatment is behaviour and lifestyle change, but adherence to such changes is limited and effect on long term outcomes has not been demonstrated.^{11,12} However, public health measures such as education and legislation will take many years to impact on the burden of established liver disease in the population. Therefore, there is a large unmet clinical need for drugs to target the pathogenic processes that drive inflammatory liver diseases.

Therefore, what is needed is a better understanding of the mechanisms that are associated with NASH in order to develop effective biomarkers of disease stage and therapeutic targets. In recent years, it has become clear that NASH is driven by a combination of metabolic dysfunction and an aberrant immuno-inflammatory response resulting in liver cell injury, and fibrosis. In a multisystem disease such as NASH, many tissues are affected and a comprehensive understanding of the disease

cannot take place without simultaneously studying the different tissues involved, including liver, fat tissue, muscle and blood. Historically such co-ordinated tissue assessment has been very difficult, but the recent rise to prominence of bariatric surgery as a metabolic treatment intervention changes that.

Bariatric surgery (increasingly referred to as 'metabolic surgery') has wide-ranging benefits on insulin sensitivity, body weight and gut hormone profile such as glucagon like peptide-1.^{13,14} Bariatric surgery is safe with morbidity and mortality comparable to hip-replacement, cholecystectomy and appendicectomy.¹⁵ Cohort studies and case series have shown benefits in both liver biochemistry and histology.¹⁶⁻¹⁸ The Lille bariatric cohort demonstrated resolution of NASH in 85% of patients with significant reduction in steatosis fibrosis.¹⁹ It is well recognised that there is marked improvement in insulin sensitivity within days post bariatric surgery driven particularly driven by reduced basal glucose production and increased hepatic insulin sensitivity.²⁰ Furthermore, immediate and dramatic changes in gut hormones such as glucagon-like peptide 1 (GLP-1) increases pancreatic insulin secretion in response to glucose and reduced glucagon production contributing to attenuation of the metabolic syndrome phenotype.^{21,22} Prior to bariatric procedures patient undergo two to three weeks of a low calorie diet which has been shown to reduce liver and intra-abdominal fat volume.^{23,24} It has been suggested this improves visibility intra-operatively, moreover, has been shown to decrease 30 day post-operative morbidity and complications.²⁵ We aim to evaluate the impact of this intervention and bariatric surgery upon serological markers and the peripheral immunophenotype.

Although only 1% of patients eligible for such operations are currently offered surgery²⁶ the prominence of metabolic surgery in international guidelines for patients with obesity, diabetes and complications means that these numbers are rising and expected to rise further. This provides an opportunity for mechanistic research such as ours.

For patients with NAFLD whom bariatric procedures are not appropriate or not under the care of bariatric services the cornerstone of management is behaviour and lifestyle change, focussing on weight loss and exercise^{12,27,28}. Weight loss reduces fatty acid supply to the liver, improves insulin sensitivity, and reduces circulating inflammatory cytokines which may be mediated by a change in the inflammatory and metabolic states of adipose tissue.²⁹

A previous meta-analysis has revealed weight loss improves steatosis and cardio-metabolic risk factors including HOMA-IR, lipid profile and glycated haemoglobin (HbA1c).³⁰ More recently, a cohort study of 293 NASH patients encouraged to adopt lifestyle changes over 52 weeks showed a dose-response between weight loss and all histological parameters of NASH with benefit seen with weight loss greater than 5%.¹²

In this study, we will collect tissue, blood, stool, urine and saliva samples at the same time in order to enable a comprehensive disease phenotyping and ability to compare immunological, microbiological and metabolic features in patients with varying stages of NAFLD and healthy controls. To date there are no published data evaluating simultaneously-obtained samples from adipose, gut and liver tissue and peripheral blood in NAFLD. The important regulatory role of adipose tissue in systemic inflammation has been highlighted previously and demonstrated a hyperactive state

in obesity.^{31,32} Therefore, a significant proportion of the participants in this study will be recruited from the bariatric surgery services so that these multiple tissue samples can be collected at time of surgery with minimal additional risk to participants.

The largest cohort of paired liver biopsies monitoring the effects of weight loss through lifestyle modification revealed that a significantly greater proportion of individuals had histological resolution of NASH if they lost greater than 5% of body weight.¹² Insulin resistance is a key component to NAFLD, therefore, the dramatic impact upon hepatic insulin resistance and gut hormones seen post bariatric surgery may display a very different pathological phenotype compared to the same amount of weight loss attained through lifestyle changes. This study will enable evaluation of these immunological, microbiological and metabolic features of NAFLD at baseline and in participants who have lost at least 5% of body weight by lifestyle interventions versus a bariatric surgery. This comparison may reveal unique insight into the pathological mechanisms in NAFLD altered by the rapid improvement of the metabolic syndrome seen after bariatric surgery independent of the amount of weight loss.

The potential benefits of this study will include identifying components which could aid disease staging; reducing the need for invasive liver biopsy but also identify those individuals at risk of disease progression with associated elevated all-cause mortality. Collecting samples from the ethnically diverse population of East and South London will enable us to evaluate risk factors and pathological characteristics which may vary between ethnic groups. Furthermore, a greater understanding of the peripheral and tissue resident inflammatory responses could highlight potential therapeutic targets for future drug development.

5.2 Risks / benefits

We do not expect any significant additional risk to participants within this study. Blood samples would amount to no more than 55mls in total, substantially less than taken at time of a blood donation, which amounts to 400mls. Tissue biopsies will only be collected from participants undergoing a planned procedure such as a liver biopsy for existing clinical purposes or gastrointestinal surgery. A large review of the safety of liver 3806 biopsies without direct visualisation but guided by ultrasound revealed a low rate of haemorrhagic complication 0.32% or hypovolaemic shock 0.11%.³³ Furthermore, the Lille bariatric cohort did not report any significant risks associated with the 1496 intra-operative liver biopsies performed within their study.¹⁹ Tissue samples taken at time of surgery have lower risk than percutaneous procedures as they are performed under direct vision of the operating surgeon with ability to ensure haemostasis post biopsy.

Participants will have an optional fine needle aspiration (FNA) of their liver at baseline and at follow up, once attaining 5%-7% weight loss. This procedure has been in use for more than 20 years as a research and clinical tool with better safety profile than standard liver biopsy.³⁴ A recent study revealed safe repeated fine needle aspiration from the same study participants with the only adverse event reported as pain post procedure requiring simple analgesia in two cases after 39 fine needle aspirates.³⁵ Furthermore, another research group has reported no serious complications in a series of more than 500 liver FNA procedures.³⁶

As part of this study if participants identified to have evidence of the more aggressive form of fatty liver disease, NASH, other liver abnormality, or signs of hepatic fibrosis they would be referred for ongoing monitoring and management and benefit from specialist advice from the Hepatology clinics at the Royal London Hospital or King's College Hospital.

6. Study objectives

6.1 Primary objective

To determine the changes in tissue-specific and peripheral immuno-inflammatory and metabolic abnormalities in NALFD in people who achieve 5% to 7% weight loss by Roux-en Y gastric bypass surgery or lifestyle measures.

6.2 Secondary objective

1. Understand the association between variations in immune-profiling and existing markers of disease activity
2. Identify which markers predict disease progression / regression after 5% to 7% weight loss

6.3 Primary endpoint

To determine differences between specific immune cell populations in peripheral blood, liver and adipose tissue between two methods of 5% to 7% weight loss.

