At the first study visit a researcher will obtain informed consent and determine that the participant meets all study inclusion and exclusion criteria to proceed. Consent will include agreeing to access NHS databases for medical information and access to existing tissue samples surplus to clinical requirements. The study researcher will guide the participant through the consent form and case report form (CRF). This will also incorporate the Short Form (36) Health Survey (SF-36) as a measure of participant self-reported health status. This is in addition to medical and drug history in addition to smoking, alcohol, dietary and exercise data. The same assessment will take place at the final study visit, once they have achieved 5% to 7% weight loss.

Data collection will include:

1. History and examination: family history, smoking and drinking habits, past medical history, drug history, demographics (race, gender, age) and life-style (quality of life, dietary, exercise and sleeping habits).
2. Anthropometric measurement including body weight, body height, waist circumference and Body Mass Index (BMI).
3. Transient elastography (Fibroscan)
4. Fasted clinical blood tests including liver function and metabolic profile.
5. Fasted research blood tests - 55mls (3 tablespoons) extra.
6. Urine, saliva and stool samples
7. Optional fine needle aspiration of the liver

Every effort will be made to arrange all study procedures at each time point in a single visit, however, if this is not possible, participants have the option to return at an alternative date for that component / those components.

If a participant is undergoing bariatric or upper gastrointestinal surgery for a non-malignant indication, a study investigator or research nurse will attend the day of their surgery and collect the tissue samples: liver and adipose tissue and gut tissue (if their operation includes bowel resection) having consented previously. All participants with NAFLD will be offered a follow up visit once they have achieved 5% to 7% weight loss with repeat assessment of immune-profile and liver specific tests. Additional consent pertaining to fine needle liver aspirate will be obtained immediately prior to this procedure. The standard NHS consent form will be used for this.

Study procedures by visit

Study intervention	Visit 1	Visit 2 (Surgical & biopsy participants only)	Visit 3 (5%-7% weight loss achieved)
Informed Consent	X		
Screening	X		
Medical history	X	X	X

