Questionnaires	X		X
Blood sample	X	X	X
Urine, stool, saliva samples	X	X	X
Liver Fibroscan	X		X
Liver Fine Needle Aspiration (Optional)	X		X
Liver Biopsy sample (If already clinically indicated)		X	
Intra-abdominal tissue sampling (At time of planned surgery)		X	

If the study procedures identify a significant liver abnormality, elevated liver function tests or elevated Fibroscan score. We will ensure the participant is informed by one of the study investigators and referred for further investigation and management within a liver clinic at either Barts Health or Kings College Hospital.

If a participant wishes to fully, or partially, withdraw from the study, they will be asked if they wish to have existing data and samples to be destroyed or whether they can be still used for the purposes of the study. Withdrawal of consent will be documented in the participants CRF.

10. Assessment and management of risk

We do not expect any significant additional risk to participants within this study. Blood samples would amount to no more than 55mls in total, substantially less than taken at time of a blood donation, approximately 400mls. Fresh tissue samples will only be collected from participants undergoing a planned procedure such as a liver biopsy for existing clinical purposes or bariatric surgery. A large review of the safety of liver 3806 biopsies without direct visualisation but guided by ultrasound revealed an exceptionally low rate of haemorrhagic complication 0.32% or hypovolaemic shock 0.11%.³³ Furthermore, the Lille bariatric cohort did not report any significant risks associated with the 1496 intra-operative liver biopsies performed within their study.¹⁹ Tissue samples taken at time of surgery have minimal risk as they are performed under direct vision of the operating surgeon with ability to ensure haemostasis post biopsy.

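### The primary endpoint compares adipose immune cells between two weight-loss methods, but no adipose is scheduled after weight loss in either group, and none at all for lifestyle participants

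*Protocol*

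**What the plan says.** The primary endpoint, in Protocol section 6.3, reads: "To determine differences between specific immune cell populations in peripheral blood, liver and adipose tissue between two methods of 5% to 7% weight loss". Section 6.1 identifies the methods as Roux-en-Y gastric bypass and lifestyle measures. Adipose is one of three compartments in a contrast between those two groups.

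The rules on collecting tissue are elsewhere in the Protocol:

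- **Section 9, text.** For participants having bariatric or other non-malignant upper gastrointestinal surgery, a member of the study team "will attend the day of their surgery and collect the tissue samples: liver and adipose tissue and gut tissue". No other source of adipose is described.
- **Section 9, visit table.** The row "Intra-abdominal tissue sampling (At time of planned surgery)" is marked only in the column headed "Visit 2 (Surgical & biopsy participants only)".
- **Section 9, follow-up.** NAFLD participants are offered a visit at 5% to 7% loss "with repeat assessment of immune-profile and liver specific tests". The Visit 3 column lists history, questionnaires, blood, urine, stool, saliva, Fibroscan and an optional liver fine needle aspirate (FNA). Adipose is not listed.
- **Sections 5.2 and 10.** Section 5.2 says "Tissue biopsies will only be collected from participants undergoing a planned procedure such as a liver biopsy for existing clinical purposes or gastrointestinal surgery". Section 10 repeats the limit: "Fresh tissue samples will only be collected from participants undergoing a planned procedure".

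**The concern.** To compare two methods of losing weight in a given tissue, that tissue is needed from both groups after the loss. For a comparison of changes it is also needed before the loss. Adipose meets neither requirement. The lifestyle route involves no operation, so it has no scheduled adipose. The bypass group has one scheduled sample, taken on the day of surgery and so before the surgery has produced any weight loss.

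One of the three compartments in the only primary endpoint would therefore have no data for the stated comparison. Two outcomes are likely if the text stays. Either a primary component goes unreported, or the day-of-surgery adipose is presented as evidence about the method of weight loss, which it cannot be. That sample is not an untreated baseline either: section 5.1 says bariatric patients spend two to three weeks on a low calorie diet before the operation.

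**Working it through.** **The plan's own figure.** The only computed number is the sample size in section 11. It can be reconstructed from the inputs given there, although the Protocol shows no formula:

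- NASH target: 40 + 40 = 80
- NAFLD participants needed at a 75% NASH rate: 80 / 0.75 = 106.7, rounded up to 107
- With 20 healthy controls: 107 + 20 = 127
- With 20% contingency: 127 × 1.2 = 152.4, rounded up to 153

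This matches the stated 153. It is built on fibrosis groups and gives no split by weight-loss method. The point below does not depend on it.

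**Scheduled samples by compartment, method and visit** (sections 8 and 9):

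| Compartment | Method | Visit 1 | Visit 2 | Visit 3 (after loss) |
|---|---|---|---|---|
| Blood | Bypass | yes | yes | yes |
| Blood | Lifestyle | yes | only if a biopsy participant | yes |
| Liver | Bypass | optional FNA | intra-operative sample | optional FNA |
| Liver | Lifestyle | optional FNA | biopsy only if clinically indicated | optional FNA |
| Adipose | Bypass | none | day of surgery | none |
| Adipose | Lifestyle | none | none scheduled | none |

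**Reading 1: difference between methods at Visit 3.** Two cells are needed, one per method.

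- Blood: 2 of 2
- Liver: 2 of 2, in those who accept the optional FNA
- Adipose: 0 of 2

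**Reading 2: difference in change from before to after the loss.** Four cells are needed (2 methods × 2 times).

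- If the day-of-surgery sample counts as the bypass baseline, adipose has 1 of 4.
- If the baseline must be Visit 1, adipose has 0 of 4.
- The two post-loss cells are empty in both cases.

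**Other possible sources of adipose in the Protocol:**

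- *Surplus tissue.* Consent covers "access to existing tissue samples surplus to clinical requirements" (section 9), but it names no adipose, time point or group.
- *Surgical healthy controls.* They have a Visit 2 with tissue collection (section 8) but belong to neither weight-loss method.
- *Pre-operative diet.* Any loss by the day of surgery comes from diet and precedes the bypass. The stated aim for that period in section 5.1 concerns serological markers and the peripheral immunophenotype, not adipose.

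None of these fills an empty cell. Because the cells are empty by design, recruiting more participants does not help.

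**The case against.** The strongest arguments on the other side are these.

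1. **The absence is not absolute.** Section 9 allows collection from any participant having upper gastrointestinal surgery, so a lifestyle participant might by chance give adipose. This is fair, and the accurate wording is that none is *scheduled*. A chance sample would not be tied to 5% to 7% loss, and there would still be no post-bypass adipose to set against it.
2. **The day-of-surgery sample may follow some weight loss.** It may, through the pre-operative diet, and the Protocol gives no figure for that loss. What is certain is that the sample does not follow weight loss by surgery, and the lifestyle group supplies nothing to compare it with.
3. **Visit 2 also yields liver tissue, which an FNA-only liver contrast leaves out.** True. That tissue is also taken before the final visit, and FNA is the only liver source at Visit 3, so restricting the contrast to FNA matches what can be compared after the loss.
4. **Other reconciliations are possible.** The sponsor could instead say where comparable adipose would come from. That would be a change of procedures and would have to be squared with the limits in sections 5.2 and 10, so it is more than a wording change.
5. **The study is exploratory, and its synopsis calls it cross-sectional.** Section 11 uses its exploratory nature to explain the lack of a power calculation. That does not extend to a primary endpoint whose data are not collected. The cross-sectional label fits adipose as a description at surgery, not as a between-method contrast.

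A separate analysis plan could not resolve the matter, since it cannot create samples.

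**Conclusion.** The point holds and must be fixed. Section 6.3 contradicts the collection schedule in section 9 and the limits in sections 5.2 and 10. After weight loss, adipose is scheduled in 0 of 2 methods. As a change it has at most 1 of 4 cells. The between-method adipose difference is inestimable at any sample size and on either reading of the endpoint.

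The conclusion rests on the schedule as written and assumes no effect size, variance or uptake rate. It concerns adipose only. Blood supports the comparison in both groups. Liver supports it in participants who accept the optional FNA; how many will do so is not stated, so the size of that comparison cannot be judged from the Protocol.

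**What to change.** Amend section 6.3 so that adipose is no longer part of the weight-loss comparison. Possible text:

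> *Between-method differences (gastric bypass versus lifestyle) in specified immune cell populations, among NAFLD participants who reach 5% to 7% weight loss: (a) in peripheral blood; (b) in liver, by fine needle aspirate, in the subset who accept it. Adipose immune cell populations are described cross-sectionally at Visit 2 only, and no claim is made about weight loss or method. Bariatric samples at that visit follow the pre-operative low calorie diet.*

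Healthy controls fall outside (a) and (b), as do participants who attend the final visit without reaching 5% loss (section 8). The 5% to 7% range follows sections 6.1 and 6.3; section 5.1 speaks of at least 5%, so the amendment should keep to one definition. As an optional clarification, section 6.1 could state that tissue-specific change refers to liver.

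The cost is a wording amendment and a narrower primary claim: adipose leaves the comparison, and the liver contrast is limited to aspirates. No sample, procedure or participant is added.
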